8.2 Clinical Laboratory Evaluations

Laboratory data will be presented using units as reported by the clinical laboratory.

The following clinical laboratory tests listed will be performed as scheduled in Appendix A.

Clinical Laboratory Test Panel	Description
Clinical Chemistry:	Alanine aminotransferase, albumin, alkaline phosphatase, bilirubin total, chloride, creatinine, glucose, potassium, carbon dioxide, calcium, uric acid, albumin, total bilirubin, lactate dehydrogenase, creatinine kinase, aspartate transaminase, amylase, lipase, and sodium
Lipid profile:	Total cholesterol, cholesterol high-density lipoprotein, cholesterol low-density lipoprotein and triglycerides

Coagulation:	Prothrombin time (PT)/INR and partial thromboplastin time (PTT) levels
Endocrinology ¹ :	Follicle-stimulating hormone (for female subjects)
Hematology:	White cell count with differential (absolute values of neutrophil, lymphocyte, monocyte, eosinophil, and basophil), red cell count, hemoglobin, hematocrit, mean corpuscular volume, and platelet count
Serology ¹ :	HIV-1/HIV-2 antibodies, hepatitis B surface antigen and hepatitis C virus antibody
Urinalysis:	Color, clarity, specific gravity, pH, leukocyte, protein, glucose, ketones, bilirubin, blood, nitrite, urobilinogen. Microscopic examination will only be performed if the dipstick test is outside of the reference range for leukocyte, blood, nitrite or protein
Urine drug screen:	Amphetamines, alcohol, barbiturates, benzodiazepines, cannabinoids, cocaine, cotinine, opiates and phencyclidine
Pregnancy test:	Serum pregnancy test at Screening only and urine pregnancy test for all other scheduled days

Additional clinical laboratory tests may be performed by the medical laboratory as part of larger standard test panels (not required for subject safety).

For hematology, chemistry and urinalysis, actual values and change from baseline will be presented in the listings and will be summarized by study part, laboratory test and visit. Values outside the normal range will be flagged in the listing. The results' relationship to the reference range will be summarized by their status (Normal, Abnormal – Low, Abnormal – High) using frequencies and percentages. Frequency tables and percentages based on the number of subjects per visit will be used to summarize tests with categorical results.

Subject listings of abnormal on-study laboratory values will be provided. Similarly, clinically significant on-study laboratory data will be presented in a second listing.

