#### 1.4. Benefit/Risk Assessment

Although SBP-9330 has not been administered to humans previously, the potential risks to human subjects associated with SBP-9330 are detailed in the Summary of Data and Guidance for the Investigator within the Investigator's Brochure.

Considering the 40-fold safety factor based on the 2-week NOAEL values of rat and dog and the projected starting human therapeutic dose range of SBP-9330 of 300-600 mg/day, the proposed starting dose of 150 mg/day is not expected to induce any potential risk or benefit to subjects participating in this study.

In addition to specific safety stopping criteria (Section 3.5), dose-escalation PK stopping criteria will be implemented such that systemic exposures in subjects do not exceed  $1/10^{th}$  of the AUC0-24hr and Cmax levels associated with the identified NOAEL of the GLP 14-day rat study.

Routine clinical assessments including hematology, chemistry, and urinalysis will be performed as a means of monitoring subject safety. Potential safety considerations were limited to minor clinical pathology alterations in glucose, albumin, total protein, triglycerides and cholesterol (total and HDL) based on nonclinical safety assessments. As such, subjects will be monitored for adverse effects related to these parameters.

Overall, the safety monitoring practices employed by this protocol (i.e., physical examination, 12-lead electrocardiogram (ECG), vital signs (including orthostatic blood pressures and pulse

<sup>1animal NOAEL in mg/kg × 0.16 (rat), 0.54 (dog)

<sup>2HED × 60 kg human subject ÷ Safety Factor of 10

Altasciences Project Number: CNO-P5-319

rate), clinical laboratory tests, Columbia-Suicide Severity Rating Scale (C-SSRS) questionnaire, and AEs) are adequate to protect the subjects' safety and should detect all expected treatment-emergent AEs (TEAEs).

There will be no direct health benefit for study participants from receipt of the study drug. An indirect health benefit to the healthy subjects enrolled in this trial is the free medical tests received at Screening and during the study.

Altasciences Project Number: CNO-P5-319

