#### **6.1.5.** Laboratory Evaluations

Laboratory evaluations will be performed as outlined in Table 1 (SAD Phase), Table 2 (MAD Phase), or Table 3 (Smoker Phase).

The laboratory evaluations to be conducted for this study are presented in APPENDIX 6. Additional clinical laboratory tests may be performed by the medical laboratory as part of larger standard test panels (not required for subject safety).

An Investigator in charge or delegate will assess each abnormal value to determine if it is clinically significant. Post-dose clinically significant laboratory values will be reported as AEs, if applicable, as judged by an Investigator or delegate.

Only test results required by the protocol and/or abnormal results will be entered in the clinical database and reported in the Clinical Study Report, based on report requirement.

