# 15. APPENDIX 6: CLINICAL LABORATORY EVALUATIONS

Clinical Laboratory Test Panel	Description
	Alanine aminotransferase, albumin, alkaline phosphatase, bilirubin total, chloride, creatinine, glucose,
Clinical Chemistry:	potassium, carbon dioxide, calcium, uric acid, albumin, total bilirubin, lactate dehydrogenase, creatinine
	kinase, aspartate transaminase, amylase, lipase, and sodium
Lipid profile:	Total cholesterol, cholesterol high-density lipoprotein, cholesterol low-density lipoprotein and
Lipid prome.	triglycerides
Coagulation:	Prothrombin time (PT)/INR and partial thromboplastin time (PTT) levels
Endocrinology  :	Follicle-stimulating hormone (for female subjects)
Hamatalagu	White cell count with differential (absolute values of neutrophil, lymphocyte, monocyte, eosinophil, and
Hematology:	basophil), red cell count, hemoglobin, hematocrit, mean corpuscular volume, and platelet count
Serology  :	HIV-1/HIV-2 antibodies, hepatitis B surface antigen and hepatitis C virus antibody
	Color, clarity, specific gravity, pH, leukocyte, protein, glucose, ketones, bilirubin, blood, nitrite,
Urinalysis:	urobilinogen. Microscopic examination will only be performed if the dipstick test is outside of the
	reference range for leukocyte, blood, nitrite or protein
Urino drug garaani	Amphetamines, alcohol, barbiturates, benzodiazepines, cannabinoids, cocaine, cotinine, opiates and
Urine drug screen:	phencyclidine
Pregnancy test:	Serum pregnancy test at Screening only and urine pregnancy test for all other scheduled days

<sup>1 Screening visit only.

Altasciences Project Number: CNO-P5-319

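### Total protein is named in Protocol 1.4 as a potential safety consideration, but neither the protocol's nor the SAP's chemistry panel includes it

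*SAP*

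**What the plan says.** Protocol 1.4 gives the reason for laboratory monitoring in three consecutive sentences. The means: "Routine clinical assessments including hematology, chemistry, and urinalysis will be performed as a means of monitoring subject safety". The signals: "Potential safety considerations were limited to minor clinical pathology alterations in glucose, albumin, total protein, triglycerides and cholesterol (total and HDL"). The consequence: "As such, subjects will be monitored for adverse effects related to these parameters". The signals come from the GLP 14-day rat study in Protocol 1.2.2.

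The tests are fixed in Protocol Appendix 6 and repeated in SAP 8.2. The SAP chemistry list opens "Alanine aminotransferase, albumin, alkaline phosphatase, bilirubin total, chloride, creatinine, glucose, potassium, carbon dioxide, calcium, uric acid, albumin, total bilirubin, lactate dehydrogenase" and closes "lactate dehydrogenase, creatinine kinase, aspartate transaminase, amylase, lipase, and sodium". Appendix 6 is the same: its second line reads "potassium, carbon dioxide, calcium, uric acid, albumin, total bilirubin, lactate dehydrogenase, creatinine" and its last "kinase, aspartate transaminase, amylase, lipase, and sodium". Both lists are complete from first entry to last, with no redaction or table break.

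On tests outside the list, Protocol 6.1.5 says: "Additional clinical laboratory tests may be performed by the medical laboratory as part of larger standard test panels (not required for subject safety"). SAP 8.2 repeats that sentence. Protocol 6.1.5 also limits database entry to results that the protocol requires and/or that are abnormal.

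**The concern.** Protocol 1.4 identifies a short list of analytes to watch and points to chemistry as one of the means. The panel then leaves one of them out. Nothing in either document explains the omission, and SAP 11 declares no changes from the protocol's analyses.

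Safety is the primary objective. Changes in laboratory results on SBP-9330 compared with placebo are part of the primary endpoint (Protocol 2; SAP Table 1). An analyte with no required result has no reliable baseline, change from baseline or placebo comparison. Protocol 3.5.2 also asks the escalation review to consider consistent laboratory shifts in two or more subjects, within or across cohorts. A modest shift in total protein could not be recognised there if nobody is required to measure it.

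**Working it through.** The plan gives no figure to reproduce here. The check sets the list in Protocol 1.4 against the panels and then counts who is affected.

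**Step 1. Coverage of the six named analytes** (Appendix 6 and SAP 8.2 agree on every row):

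| Analyte named in Protocol 1.4 | Required test? | Where |
|---|---|---|
| Glucose | Yes | Chemistry |
| Albumin | Yes | Chemistry (listed twice) |
| Total protein | **No** | – |
| Triglycerides | Yes | Lipid profile |
| Total cholesterol | Yes | Lipid profile |
| HDL cholesterol | Yes | Lipid profile |

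Five of six are covered. The only protein entry in any panel is in the urinalysis dipstick list. In 1.4, total protein stands beside albumin among clinical pathology findings, so a blood measurement is the natural reading and urine protein does not replace it.

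**Step 2. Size of the chemistry list.** There are 19 entries. Albumin appears twice and total bilirubin appears twice (once with the words reversed), so 19 − 2 = 17 distinct analytes.

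**Step 3. Could total protein be collected by another route?**
- Larger laboratory panels (Protocol 6.1.5): optional, and described as not needed for safety. A normal value obtained this way need not be entered, so any abnormal values would lack a denominator.
- Investigator-added assessments (Protocol 6.1): made at discretion, as needed.
- Reporting a clinically important within-range shift as an AE (Protocol 7.1): possible only if the test was run.

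None of these produces data by cohort and visit.

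**Step 4. Subjects without a required result** (active : placebo):
- Part A: 5 × (6:2) = 30:10
- Part B: 3 × (8:2) = 24:6
- Part C: 2 × (8:2) = 16:4
- Planned total: 70:20 = 90
- With optional cohorts B4 and C3: 30:10 + 32:8 + 24:6 = 86:24 = 110, which matches the maximum in Protocol 3.3.

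**Step 5. Existing laboratory draws per subject** (footnotes to the schedules of activities):
- A1, A2, A4, A5: Screening, Day -1, pre-dose, 48 h, follow-up = 5
- A3: 4 in Period 1 (no follow-up) + 4 in Period 2 (no screening) = 8
- Parts B and C: Screening, Day -1, Days 1, 3, 7, 14 and 16, follow-up = 8

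**Step 6. A side effect.** The albumin/globulin ratio was altered in the GLP rat study and increased in the rat combination study with nicotine (Protocol 1.2.2). The panel has neither total protein nor globulin, so the ratio cannot be derived from albumin alone.

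**The case against.** The strongest reply is that no commitment is broken. Protocol 1.4 speaks of monitoring for adverse effects related to the parameters, not of assaying each one. AE monitoring runs through the study, and five of the six analytes are drawn. The primary endpoint names no analyte, and Protocol 6.1.5 makes Appendix 6 the definition of the laboratory evaluations, so a test outside that list is not strictly a missing part of the endpoint.

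The signal is also weak. The rat changes were called minor at a dose judged to be the NOAEL. The combination study does not list total protein, and its chemistry findings stayed inside the historical control range and reversed. No stopping rule specifies total protein, and the safety analysis is descriptive (Protocol 8.3.3). Counts of zero out of 90 or 110 follow automatically from one missing list entry; they measure reach, not bias or lost precision. The SAP only copies Appendix 6, so the defect originates in the protocol.

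Most of this stands and limits the weight of the point. It does not explain why the protocol singles out an analyte and then requires no result for it. Rewording 1.4 would remove the inconsistency on paper but leave the data uncollected.

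One further limit is fair. The documents do not say which cohorts had been dosed when the current versions were issued, and Part C may start only after MAD dosing is complete. A panel change cannot create required results for cohorts already finished.

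**Conclusion.** The concern holds. One of the six analytes that Protocol 1.4 names has no required result at any visit, for any of the 90 planned subjects or the 110 maximum. No systematic change from baseline or comparison with placebo is therefore assured for it. The consequence is modest: a gap in descriptive safety data for one analyte, with no effect on any test, estimate or specified stopping threshold. It merits correction because the trial is first-in-human with safety as its primary objective, and because the correction is cheap.

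This rests on reading total protein in 1.4 as a blood measurement and on following the panels exactly as written. The site's laboratory may in practice run total protein within a larger panel, but the documents do not require it. The duplicated entries suggest an editing slip; what was intended cannot be known from the documents.

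**What to change.** Add total protein to the chemistry panel in Protocol Appendix 6, and carry the change into SAP 8.2, at the laboratory draws already scheduled. As separate tidying, delete the second albumin and second total bilirubin entries. SAP 8.2 already summarises chemistry as actual values and change from baseline by study part, test and visit, so no analysis text changes. If the omission was deliberate, Protocol 1.4 should say so and state which measured analytes serve instead.

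The cost is one more routine chemistry result per existing draw: 5 per subject in Cohorts A1, A2, A4 and A5, and 8 per subject in Cohort A3 and Parts B and C. For subjects who complete, not counting screen failures, the planned cohorts need 32 × 5 + 8 × 8 + 30 × 8 + 20 × 8 = 624 results. The two optional cohorts add 20 × 8 = 160, giving 784. Cohorts already dosed would be outside the change and would lower these totals. There is no new visit or procedure. One assumption must be confirmed with the laboratory: that the existing chemistry sample volume suffices. The documents give neither a volume per laboratory tube nor a price per test.

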- 19. Parts A and B only: Positive test result for alcohol and/or drugs of abuse at Screening or prior to the first drug administration
- 20. Positive test results for HIV-1/HIV-2 antibodies, hepatitis B surface antigen (HBsAg) or hepatitis C antibody (HCVAb)

Altasciences Project Number: CNO-P5-319

- 21. Consumption of any prescription drugs (with the exception of hormonal contraceptives or hormone replacement therapy) or over-the-counter (OTC) medications and nutrients known to modulate cytochrome P450 (CYP450) enzymes activity (e.g., grapefruit or grapefruit juice, pomelo juice, star fruit, or Seville [blood] orange products) or St. John's Wort within 14 days prior to the first study drug administration
- 22. Consumption of other prescription and over-the-counter medication not specifically excluded by Exclusion Criterion 21 including health supplements and herbal remedies within 7 days prior to the first study drug administration (an exception is made for paracetamol [acetaminophen], which is allowed up to admission to the clinic).
- 23. Any other clinically significant abnormalities in laboratory test results at Screening that would, in the opinion of an Investigator, increase the subject's risk of participation, jeopardize complete participation in the study, or compromise interpretation of study data
- 24. Intake of an investigational product in the 30 days or 5 half-lives (whichever is longer) prior to Screening
- 25. Inclusion in a previous cohort of this clinical study
- 26. Employee of the contract research organization (CRO) or the Sponsor.
- 27. Blood donation (excluding plasma donation) of approximately 500 mL within 56 days prior to Screening
- 28. Plasma donation within 7 days prior to Screening

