2 STUDY OBJECTIVES

The objectives of the study and corresponding study endpoints are detailed in Table 1.

Table 1: Objectives and related endpoints

Objective	Endpoint	Analysis
Primary		
To assess the safety and tolerability of single and multiple ascending oral doses of SBP-9330 in healthy nonsmokers and healthy smokers	
 Incidence and severity of adverse events (AEs) for subjects administered SBP-9330 compared to placebo Changes in vital signs, physical examination findings, ECG findings, C-SSRS questionnaire results, and clinical laboratory results for subjects administered SBP-9330 compared to placebo 	Refer to Section 8
Secondary		
To determine single and multiple oral dose pharmacokinetics (PK) of SBP-9330 in healthy nonsmokers and healthy smokers	
Pharmacokinetic (PK) parameters, where appropriate, will be determined for SBP-9330 from individual concentration-time profiles in plasma.
 
The following PK parameters will be evaluated for each study phase:
 
Part A (SAD Phase):
 
 C_{max}, T_{max}, AUC_{0-24}, AUC_{0-T}, $AUC_{0-\infty}$, T_{half}, CL/F, and V_z/F 
Part B (MAD Phase) and Part C (Smoker Phase):
 
 Day 1: C_{max}, T_{max}, AUC_{0-24}, AUC_{0-T} Days 7, 11, 12, and 13: C_{trough} Day 14: C_{trough}, C_{max}, T_{max}, C_{τ}, AUC_{τ}, AUC_{0-T}, effective T_{half}, CL/F_{ss}, V_z/F_{ss}, $RAC(C_{max})$, $RAC(AUC)$ 
For all study parts, additional PK parameters will be estimated for supportive purposes.
	Refer to Section 7
To explore the effect of food on the single oral dose PK of SBP-9330 in healthy nonsmokers	
Main PK parameters will be determined to assess the effect of food after a single oral dose of 600 mg SBP-9330.
 
For Cohort A3 (Food Effects) only, the PK parameters specified above for Part A will be estimated on Day 1 and Day 8. Inferential statistical analysis will be performed on the following main PK parameters:
 
 C_{max}, AUC_{0-T}, and $AUC_{0-\infty}$ 
In addition, T_{max} will be summarized descriptively
	Refer to Section 7

Exploratory		

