8 SAFETY ANALYSIS

Unless otherwise specified, all available data will be listed and summary tables for safety assessments will be presented for the safety population as detailed in Table 8.

Table 8: Data presentations for safety assessments

Data	Variables	Presentation
Adverse events	Adverse event (AE) description, onset and resolution date and time, time from product use, severity, relationship to study drug, action taken, and outcome	
Listing (by subject, Cohort and treatment): L16.2.7.1
 
Summary tables, including number and percentage of subjects experiencing:
 
 • Reported AEs, • Treatment-emergent adverse events (TEAEs), • Drug-related TEAEs (i.e. those with a relationship classified as Definite, Probable, Possible and Unlikely), • TEAEs by relationship to study treatment (i.e., Definite, Probable, Possible, Unlikely and Not related), • TEAEs by severity, • Serious TEAEs, • Study drug-related serious TEAEs, • TEAEs leading to withdrawal, and • TEAEs with an outcome of death. 
Note: includes coded terms (system organ class [SOC] and preferred term [PT]) T14.3.1.1.1 – T14.3.1.4.4, T14.3.2.1 and T14.3.2.2

Concomitant medications	All medications taken during the study (as defined in the protocol and including prior medications that are continued), dose, units, frequency, formulation, route, indication/ reason taken, and date and time	
Listing
 
Note: includes coded terms (anatomic therapeutic chemical [ATC] level 1 and preferred name)
 
L16.2.7.2

Extent of exposure	Category of drug, treatment, total dose, dose unit, formulation, frequency, administration date and time, route of administration, Was the treatment administered as specified in the protocol? and dosing comments	
Listings:
 
L16.2.5.1
 
L16.2.5.2
 
L16.2.5.3

Clinical laboratory	Laboratory results (refer to section)	Listings:

Data	Variables	Presentation
evaluations	9.2 for parameters)	
 • All laboratory values by visit L16.2.8.1.1 – L16.2.8.1.7 • All out-of-range laboratory values • All clinically significant laboratory values T14.3.4.1.1 – T14.3.4.1.2 
Summary tables
 
 • Summary of continuous tests • Summary of categorical tests 
T14.3.4.2.1 – T14.3.4.5.4

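### SAP 8.2 tabulates laboratory Normal/Low/High status without baseline status, so the number of subjects who become out of range after dosing is not a specified output

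*SAP*

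**What the plan says.** The primary endpoints in SAP section 2 include changes in "clinical laboratory results for subjects administered SBP-9330 compared to placebo". Protocol 8.3.1 adds that laboratory abnormalities will be assessed.

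For hematology, chemistry and urinalysis, SAP 8.2 plans three things:

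- Numeric results: "actual values and change from baseline will be presented in the listings and will be summarized by study part, laboratory test and visit".
- Reference range: the results' "relationship to the reference range will be summarized by their status", in the categories Normal, Abnormal – Low and Abnormal – High.
- Tests with categorical results: "Frequency tables and percentages based on the number of subjects per visit".

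SAP 8.2 also states: "Subject listings of abnormal on-study laboratory values will be provided". A second listing covers clinically significant values. SAP Table 8 names two kinds of laboratory summary table, one for continuous tests and the other a "Summary of categorical tests". SAP 9.3 defines baseline as the last non-missing evaluation before the first dose. For laboratory data the SAP uses it only for change from baseline.

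**The concern.** Subjects can enter the study with out-of-range results. Exclusion criterion 23 in Protocol 4.2 removes only "Any other clinically significant abnormalities in laboratory test results at Screening" that the Investigator considers would raise risk, jeopardize participation or compromise interpretation. A minor deviation at baseline that persists is then counted as abnormal after dosing, in the same cell as a value that moved out of range on treatment.

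With 6 or 8 active subjects per cohort, a reader who wants to know how many subjects moved out of range on each dose, compared with placebo, cannot get this from the planned status table. The question is a natural one here. Protocol 1.4 names glucose, albumin, total protein, triglycerides and cholesterol as the potential safety considerations, and Protocol 3.5.2 itself speaks of laboratory changes in two or more subjects.

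**Working it through.** The documents give no figure to reproduce on this point; SAP 3.2 says the sample size has no statistical basis. The check has four steps.

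**1. Search for the missing output.** SAP Table 8 and sections 8.2, 9.1, 9.3, 9.4 and 11, and Protocol 6.1.5 and 8.3.1 to 8.3.3, contain no table of post-baseline against baseline status, no count restricted to subjects normal at baseline, and no count of subjects with any new abnormality.

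**2. What status counts can and cannot give.** With n subjects, b High at baseline and p High after dosing, the number newly High lies between max(0, p − b) and min(p, n − b).

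- n = 8, b = 2, p = 2: from max(0, 0) = 0 to min(2, 6) = 2.
- n = 8, b = 1, p = 2: from 1 to 2.

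If the table is laid out by visit, counts also do not add up to subjects. Part B has five post-baseline samplings (Days 3, 7, 14 and 16, and follow-up; Protocol Table 2). If each shows 1 of 8 High, the number of distinct subjects ever High is anywhere from 1 to 5.

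**3. How easily a pre-existing abnormality enters a cell.** One subject is 1/6 = 16.7% or 1/8 = 12.5%. Let q be the chance that a subject is out of range at baseline on one test. The documents give no q, so a range is assumed. The chance of at least one such subject is 1 − (1 − q)^n:

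| q | n = 6 | n = 8 |
|---|---|---|
| 2.5% | 14.1% | 18.3% |
| 5% | 26.5% | 33.7% |
| 10% | 46.9% | 57.0% |

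**4. Illustration with no drug effect.** Assume one normally distributed analyte, a 95% reference range (limits ±1.96) and an equal correlation r between any two visits. None of this is in the documents.

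- Share of post-dose out-of-range results already out on the same side at baseline: 2·P(Z1 > 1.96, Z2 > 1.96)/0.05 = 18.5%, 33.1%, 43.9% and 59.3% for r = 0.5, 0.7, 0.8 and 0.9.
- Out of range at least once over five post-baseline visits: 1 − P(all five in range) = about 18% (r = 0.5) to 10% (r = 0.9), against 5% at any single visit. This includes subjects already abnormal at baseline.
- Newly out of range among baseline-normal subjects: 1 − P(all six in range)/P(baseline in range) = 1 − 0.7927/0.95 = 16.6% (r = 0.5), and 1 − 0.8918/0.95 = 6.1% (r = 0.9).
- At least one newly abnormal subject among 8 normal at baseline: 1 − (1 − 0.166)^8 = about 76% (r = 0.5), and 1 − (1 − 0.061)^8 = about 40% (r = 0.9), per analyte.

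**The case against.** The other side has five good arguments.

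- **The endpoint is largely covered.** It is worded as changes in laboratory results, and the change-from-baseline summaries address that directly. A count of newly abnormal subjects is not a named endpoint, and Protocol 8.3.3 promises only descriptive statistics. This stands. A reader might infer that part of the primary endpoint is never produced; the documents do not support that.
- **A single large shift is not hidden.** It is tempting to say that one marked change among 6 to 8 subjects is averaged away. But SAP 9.1 uses PROC UNIVARIATE and sets display rules for minima and maxima, including for derived variables, so an extreme change appears there and in the listings. This stands. Minimum and maximum show the size of the most extreme change, though, not how many subjects crossed a limit.
- **Important new abnormalities are counted.** Under Protocol 6.1.5, clinically significant post-dose values become adverse events, if applicable, and reach the treatment-emergent tables. This stands and narrows the gap to new out-of-range values not reported as adverse events.
- **The layout is not stated.** The status sentence does not mention visits; the sentences on either side do. If the table is by visit, it would probably carry the pre-dose rows (Day -1 and Day 1), so a baseline imbalance between a dose group and placebo would be visible. A reader might infer that such an imbalance would go unseen; that is not established. The within-subject link is lost under either layout.
- **Table layouts are in a separate document** (SAP section 12). A shift table there cannot be ruled out, so the claim is limited to what the SAP text specifies.

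Listings would allow a hand count. A tabulation outside the plan made after database lock or unblinding would, however, be labeled post hoc under SAP section 9.

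**Conclusion.** The point holds in limited form. The SAP's status summary mixes pre-existing and new out-of-range values, and the SAP text specifies no output that gives the number of subjects who become Low or High. The uncounted part is new out-of-range values not reported as adverse events.

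The arithmetic in steps 1 and 2 needs no assumption beyond the counts chosen as examples and, for the distinct-subject count, a by-visit layout. The probabilities in steps 3 and 4 rest on an assumed baseline rate and an assumed normal model. They show that the issue is plausible in groups of 6 to 8, and they are not predictions for this trial. In particular, the 19% to 59% and 10% to 18% ranges do not measure how many new abnormalities the plan would miss.

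A reader might also infer that dose-escalation decisions are affected. The documents do not support this: SAP section 10 describes only PK output for those reviews and does not tie the SAP 8.2 tables to them. The weakness is in final reporting, and it is minor and cheap to remove.

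**What to change.** Add to SAP 8.2 and SAP Table 8, for each analyte, a shift table of baseline status (SAP 9.3 definition) by worst post-baseline status in each direction. Present it by dose group and pooled placebo within each study part. Show the number and percentage of subjects newly Low and newly High. For each direction, the denominator should be subjects with a baseline and at least one post-baseline value who were not already out of range in that direction.

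Say in the same edit whether the status summary is by visit. Also say whether it covers the lipid and coagulation panels: the 8.2 summary sentence names only hematology, chemistry and urinalysis, while Protocol 1.4 lists triglycerides and cholesterol as items to watch.

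The cost is a few more tables from data already collected, with no change to conduct. The trade-off is that taking the worst of several visits produces chance entries (6.1% to 16.6% of baseline-normal subjects per analyte in the illustration). The counts must therefore be read against pooled placebo, which is itself small: 2 subjects per cohort, hence 6 or 8 in Part B and 4 or 6 in Part C.
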